Patients will come off study at the time of radiographic (CT and/or bone scintigraphy) disease progression, with progression being defined only AFTER the first 3-month staging evaluation, at the time of undue toxicity (as defined below), or at the discretion of the patient and treating physician that continuing treatment is not in the best interest of the patient and/or that other standard therapies for prostate cancer are warranted due to symptomatic progression. Patients should be discouraged from discontinuing protocol treatment for PSA rise only. NaF and FLT PET/CT scans will be investigational and will not be used for making individual subject treatment decisions with respect to progression necessitating continuing or discontinuing protocol treatment. However, findings on NaF or FLT PET/CT that might pose medical risk to individual subjects will be communicated to the treating physician such that dedicated clinical imaging/intervention could be pursued, if necessary. Such findings on NaF or FLT PET/CT, by themselves, will not be used to define disease progression necessarily requiring patients to come off trial. Patients who, in the discretion of the treating physician, appear to be benefiting (e.g. declining serum PSA and/or

improvement in symptoms despite new radiographic lesions), may continue in protocol treatment/observation after discussion with the PI and study sponsor. Patients will continue to have blood drawn for immune studies, as per study calendar, up to one year after screening, even if off study prior to that time. Patients who undergo an initial research biopsy and/or NaF/FLT PET scan should also undergo the subsequent scans, as long as they are willing, even if they are off study prior to Month 3. In particular, evaluations performed at 6-month time point should be performed even if off-study prior to that time, if feasible. All subjects who have not come off study earlier for these reasons will come off study at the end of one year.

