The primary endpoints of the trial will be clinical endpoints (safety, 6 month PFS, and objective response rates). All subjects will undergo radiographic imaging (CT of abdomen and pelvis and bone scan) prior to treatment, and at 3-month intervals (or as clinically indicated). Radiographic disease progression and response will be defined using PCWG2 published criteria [65], and as detailed in Section 7. Based on the prior trials leading to the approval of sipuleucel-T, and because immune therapies are expected to require up to several months before radiographic responses or stabilization might be observed, the radiographic studies obtained at 3 months will not be used to define progression, rather will be used as the baseline for future comparison. That is, while baseline studies will be obtained prior to study registration, and radiographic progression may be expected in 50% of patients at 3 months, this will not be used to define progression necessitating patients come off study, rather disease progression occurring after this initial 3-month period. These criteria, in addition to being more standard for contemporary clinical trials in advanced prostate cancer, were also specifically designed to capture late radiographic objective responses that have been observed with immune-based therapies, including pembrolizumab and other T-cell checkpoint inhibitors [80]. Time to progression will be determined from registration for all subjects. 6-month progression-free survival will be calculated for each treatment arm, as well as the median progression-free survival.

The primary endpoint for the extended treatment Arms 3 and 4 will be time to radiographic progression.

7. Measurement of Effect (PCWG2 Recommendations)

A. Malignant Disease Evaluation

To assess objective response, it is necessary to estimate the overall tumor burden at baseline (for purposes of comparison, “baseline” imaging will be that obtained at 3-month time point) to which subsequent measurements will be compared. Measurable disease is defined by the presence of at least one measurable lesion.

All measurements should be recorded in metric notation by use of a ruler or calipers. The same method of assessment and the same technique should be used to characterize each identified lesion at baseline and during follow-up. All pre-treatment evaluations should be performed as closely as possible to the beginning of treatment and not more than four weeks before registration.

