The term evaluable in reference to measurability will not be used because it does not provide additional meaning or accuracy.

At baseline, tumor lesions will be characterized as either measurable or non-measurable.

NOTE: While progression will be documented from pre-treatment staging studies in all individuals, the intent of these measurements in this trial will be to determine whether “baseline” evaluation for immune-based treatments is preferable at a later time point after the therapy has been given the opportunity to exert an anti-tumor effect. Hence, the “baseline” evaluation for determining progression will be the staging studies performed ~ day 85 (3 months). Objective progression at that time point (Month 3, day 85) from the pre-treatment scans will not be used to alter treatment unless the patient has symptomatic disease requiring other therapy and thereby needs to discontinue treatment. For all of these measurements, PCWG2 criteria will be used to identify “measurable” lesions at each of the baseline (pre-treatment and 3 month time points), and RECIST 1.1 criteria will be used to monitor for change over time (consistent with PCWG2 criteria).

1. Measurable

Lesions that can be accurately measured in at least one dimension (longest diameter to be recorded) as ≥ 20 mm (2.0 cm) with conventional techniques or as > 10 mm (1.0 cm) with **spiral** CT scan. For a lymph node to be considered pathologically enlarged and measurable, it must be ≥ 15 mm in short axis when assessed by spiral CT.

If the measurable disease is restricted to a solitary lesion, its neoplastic nature should be confirmed by cytology/histology.

Tumor lesions that are situated in a previously irradiated area are not considered measurable.

2. Non-Measurable

All other lesions, including small lesions [longest diameter < 20 mm (2.0 cm) with conventional techniques or < 10 mm (1.0 cm) with **spiral** CT scan], lymph nodes < 15 mm in short axis, and truly non-measurable lesions.

Lesions considered to be truly non-measurable include the following: bone lesions, leptomeningeal disease, ascites, pleural/pericardial effusion, lymphangitis cutis/pulmonis, abdominal masses that are not confirmed and followed by imaging techniques, and cystic lesions.

B. Definitions of Response

1. Target Lesions

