All measurable lesions, up to a maximum of two lesions per organ and five lesions in total, representative of all involved organs. Target lesions should be selected on the basis of their size (those with the largest diameters) and their suitability for accurate repeated measurements.

The sum of the diameters (long axis for non-nodal, short axis for nodal) of all target lesions will be calculated at baseline and reported as the baseline sum diameter. The sum diameter will be used to characterize the objective tumor response.

a. Complete Response (CR)

The disappearance of all target lesions. To be assigned a status of complete response, changes in tumor measurements must be confirmed by repeat assessments performed **no less than four weeks** after the criteria for response are first met. PSA must also be ≤ 0.2 ng/mL. All disease must be assessed using the same technique as at baseline. Lymph nodes that shrink to less than 1.0 cm are considered normal.

b. Partial Response (PR)

At least a 30% decrease in the sum of the diameters of target lesions (long axis for non-nodal lesions, short axis for nodal lesions), taking as reference the baseline sum diameter. To be assigned a status of partial response, changes in tumor measurements must be confirmed by repeat assessments performed **no less than four weeks** after the criteria for response are first met. There must be no new lesions. All target measurable lesions must be assessed using the same techniques as at baseline.

c. Progressive Disease (PD)

At least a 20% increase in the sum of the diameters of target lesions (long axis for non-nodal lesions, short axis for nodal lesions), and a 0.5 cm absolute minimum increase, taking as reference the smallest sum diameter recorded since the Month 3 baseline measurements, or the appearance of one or more new lesion(s).

d. Stable Disease (SD)

Change in tumor size is less than that required to identify a partial response or progressive disease. To be assigned a status of stable disease, measurements must have met the stable disease criteria at least once after study entry at a minimum interval of 12 weeks.

2. Nontarget Lesions

All other lesions or sites of disease that do not meet the criteria for target lesions, including those on bone scintigraphy. Measurements of these lesions are not required, but the presence or absence of each should be noted throughout the study.

a. Complete Response (CR)

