A total sample size of 20 evaluable patients is proposed for the extended treatment Arm 3 to evaluate the median time to radiographic progression. The proposed concurrent administration schedule will be considered as ineffective if it results in a median time to radiographic progression of 3 months or less. Hence, the null hypothesis that the median time to radiographic progression is at most 3 months will be tested against the alternative hypothesis that the median is greater than 3 months. A median time to radiographic progression of 6 months or more, on the other hand, will be considered as promising to warrant further clinical evaluation of the proposed concurrent administration schedule. With the proposed sample size of 20 evaluable patients for the extended treatment Arm 3, a median time to radiographic progression of 6 months will be detected with 90% power at the one-sided 0.05 significance level, assuming an accrual period of 12 months with a uniform accrual pattern and a minimum follow-up period of 12 months. Furthermore, a total sample size of 20 evaluable patients is also proposed for the extended treatment Arm 4, to evaluate the median time to radiographic progression for this study arm. The null hypothesis that the median time to radiographic progression is at most 3 months will be tested against the alternative hypothesis that the median is greater than 3 months. With the proposed sample size of 20 evaluable patients for the extended treatment Arm 4, a median time to radiographic progression of 6 months will be detected with 90% power at the one-sided 0.05 significance level, assuming an accrual period of 12 months with a uniform accrual pattern and a minimum follow-up period of 12 months. Furthermore, the proposed sample size of 20 patients for both Arm 3 and Arm 4 is adequate to estimate toxicity rates within each arm with sufficient accuracy. Specifically, toxicity rates will be estimated with a standard error of less than 12% and the corresponding two-sided 95% confidence intervals will be no wider than 40%.

NaF PET/CT will be obtained in 6 - 10 patients with known osteoblastic metastases at baseline, week 6 and week 12. This sample size will provide at least 80% power to detect moderate to large effect sizes ranging from 1.0-2.0 for the differences in SUV metrics between time points at the two-sided 0.05 significance level.

F. Analysis

F.1. General

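### The 3-month null for Arms 3 and 4 has no designated clock, reference scan or test; if the registration clock is paired with the Month-3 baseline, the null is close to excluded by construction

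*Combined protocol and SAP*

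**What the plan says.** Section 6.B sets the endpoint: "The primary endpoint for the extended treatment Arms 3 and 4 will be time to radiographic progression". Section 11.E states that "the null hypothesis that the median time to radiographic progression is at most 3 months will be tested against the alternative hypothesis" of a longer median, and F.4.2 repeats this null. Section 11.E adds 20 evaluable patients per arm and 90% power at a 6-month median, one-sided 0.05. Neither section attaches a clock, a reference scan or a test to this null.

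Other sections supply several candidates.

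- **Clock.** Section 6.B: "Time to progression will be determined from registration for all subjects". Section 7.C.5 gives two definitions, one from randomization and one from the 3-month assessment, with death as an event in both. F.4.2 plans both analyses and ranks neither.
- **Reference scan.** Section 6.B says that "the radiographic studies obtained at 3 months will not be used to define progression, rather will be used as the baseline for future comparison". Section 7.B.1.c defines progressive disease "taking as reference the smallest sum diameter recorded since the Month 3 baseline measurements". The note in 7.A nevertheless says that "progression will be documented from pre-treatment staging studies in all individuals".
- **Test.** F.4.2 assigns the log-rank test to Arm 1 versus Arm 2. For the medians of all four arms it names Kaplan-Meier estimates with Brookmeyer-Crowley 95% intervals.

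Randomization covers only the first two arms (11.D), so Arms 3 and 4 have no randomization date. F.1 promises a detailed SAP before the final data are analysed.

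**The concern.** This null is the only formal efficacy test in the extended arms (2 × 20 = 40 evaluable patients). A test of a median means something only when the clock and the baseline scan belong together. If time runs from registration but radiographic progression cannot be declared until after the Month-3 scan, nearly 3 months are credited to every patient who survives that long. Rejecting a 3-month median would then say little about treatment.

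The 3-month figure itself comes from the other pairing. Section 2.F puts the median time to progression at this stage of disease on the order of 3 months, and 6.B expects progression in 50% at 3 months relative to the pre-treatment scans. The arms are open-label, so the choice should be on paper before their progression data are reviewed.

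**Working it through.** **Inputs.** From 11.E: n = 20, medians 3 versus 6 months, one-sided 0.05, uniform accrual over 12 months, minimum follow-up 12 months. From the Arm 3 and 4 schedules: scans at Weeks 12, 24, 36 and 48. From 7.C.5: death is an event. Assumptions of this check: exponential times, the share of deaths before the Week 12 scan, and the residual median after Month 3.

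**1. The plan's own figure.** At a 6-month median the hazard is λ = ln2/6 = 0.1155 per month.

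- P(event) = 1 − (e^(−12λ) − e^(−24λ))/(12λ) = 1 − (0.25 − 0.0625)/1.386 = 0.865, so 20 × 0.865 = 17.3 events are expected.
- Power = Φ(√17.3 × ln(6/3) − 1.645) = Φ(2.883 − 1.645) = Φ(1.238) = 0.89.

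Simulation also gives 0.89, for the exponential and for the one-sample log-rank test. The stated 90% holds with exact event times and events possible from time zero.

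**2. Earliest event under the mixed pairing** (registration clock, Month-3 baseline). Week 12 is 84/30.44 = 2.76 months, or 77/30.44 = 2.53 if the scan is 7 days early. Week 24 is 168/30.44 = 5.52 months. Any gap between registration and Day 1 adds to these. Only deaths can come earlier than Week 12; clinically indicated scans can shorten only the wait after it.

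**3. What the null would then require.** With no early deaths and residual median m, the median from registration is 2.76 + m. A median of at most 3 months needs m ≤ 0.24 months, about 7 days. With 20% early deaths it needs 0.20 + 0.80 × (1 − 2^(−0.24/m)) ≥ 0.50, so 2^(−0.24/m) ≤ 0.625 and m ≤ 0.35 months. With scheduled scans only, half the patients would have to die within 3 months.

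**4. Rejection rates under the mixed pairing.** 40,000 simulated arms of 20, followed to Week 48. With d events and total follow-up T, reject if √d × ln[(T/d) × ln2/3] > 1.645. Each cell gives immediate detection, then scheduled scans only.

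| Residual median | No early deaths | 10% | 20% |
|---|---|---|---|
| 3 months | 84% / 99.9% | 63% / 96% | 40% / 80% |
| 2 months | 24% / 96% | 11% / 72% | 5% / 41% |

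A one-sample log-rank test agrees within 1 percentage point.

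**5. Matched pairings, true median 3 months.** With exact times the exponential test rejects in 3.6% (pre-treatment baseline, registration clock) and 3.5% (Month-3 baseline, Month-3 clock). If scan dates are treated as exact event times, each event is dated late by up to 12 weeks, and rejection rises to 29% and 28%.

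**6. A grouped test.** Count 12-week intervals passed or failed. The chance of passing one is 2^(−2.76/3) = 0.529 at a 3-month median and 2^(−2.76/6) = 0.727 at 6 months. The first value implies 47% progressed by Week 12, in line with the 50% in 6.B. A signed likelihood-ratio test on these counts gives size about 4% and power 87% for the pre-treatment pair, and 4.6% and 84% for the Month-3 pair. Under the mixed pairing (residual median 3 months) the same test still rejects in 89% with no early deaths and 44% with 20%, so a better test does not by itself repair the pairing.

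**The case against.** No analysis section prescribes the mixed pairing. F.4.2 and 7.C.5 describe two analyses, each of which can be read with clock and baseline matched, and the 7.A note keeps the pre-treatment scans in play. Part of 6.B concerns leaving study: "progression being defined only AFTER the first 3-month staging evaluation" sits in the off-study rules, and a companion sentence says of early progression that "this will not be used to define progression necessitating patients come off study, rather disease progression occurring after this initial 3-month period". This stands, so the floor is conditional on one reading. But the registration clock, the Month-3 baseline in 6.B and the reference in 7.B.1.c are not worded as off-study rules. Following them together gives exactly the mixed pairing.

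The plan also describes a pilot, commits to reporting both baselines and promises a detailed SAP. That limits selective reporting and means the gap can still be closed. It does not say which result decides the null. The Arm 4 amendment described in 2.F cites PSA, immune and toxicity data, not Arm 3 radiographic progression, so it is no sign that a clock would be chosen to suit the outcome.

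Finally, the step 4 range, 5% to 99.9%, depends on assumed residual medians and early deaths, and the simulations omit the bone-scan confirmation rule in 7.B.2. Both points are fair. The floor in steps 2 and 3 does not depend on the simulations.

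**Conclusion.** The concern holds as a failure to designate, with one available reading that nearly settles the test in advance. Under that reading an exponential test rejects in 84% to 99.9% of arms with no early deaths and in 40% to 80% with 20%, at a residual median of 3 months; at 2 months the rates are lower, especially with immediate detection. It should be settled before Arm 3 and 4 progression data are reviewed.

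A reader might infer more than the documents support:

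- *That 84% to 99.9% is the type I error.* It is not. With a residual median of 3 months and no early deaths, the median from registration is 2.76 + 3 = 5.76 months, so the null as worded is false. The figures show that the null is badly placed for that definition.
- *That the plan requires the mixed pairing.* It does not; matched pairings are permitted and are calibrated with exact times.
- *That the 90% power is wrong.* It reproduces at 0.89 for the test and timing in step 1.
- *That Brookmeyer-Crowley is the test, with lower power.* Inverting a one-sided 5% linear bound would give about 64% with exact times, but F.4.2 names the method only for intervals.

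**What to change.** In 11.E and F.4.2, for Arms 3 and 4:

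1. State that the registration clock with the Month-3 baseline is not used for the 3-month null.
2. Designate as primary the pre-treatment baseline with the clock from registration. Count progression at Week 12 as an event for analysis only. Sections 2.F and 6.B tie the 3-month figure to this pairing.
3. Report the Month-3 baseline with the clock from the Month-3 assessment (definition 2 in 7.C.5) as secondary.
4. Replace randomization by registration for these non-randomized arms.
5. Name the test and restate its power for 12-week scan intervals. The grouped exponential likelihood-ratio test in step 6 is one example (size about 4%, power about 87%). Say how bone lesions awaiting confirmation are dated.

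The cost is wording and analysis work, with no extra scans or patients and no change to treatment continuation. Stated power falls slightly from 90%, and the example test adds a parametric assumption. The secondary analysis loses patients who die or leave before Month 3: its power is 84% with 20 patients, 81% if 18 reach that scan and 77% if 16 do.

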The following section describes the schedule for prescreening, treatment, and clinical and laboratory evaluations. When a chemistry panel is indicated the following tests are performed: Chem 7 (including sodium, potassium, bicarbonate, BUN, creatinine, and glucose), ALT, AST, bilirubin, alkaline phosphatase, amylase, thyroid stimulating hormone (TSH) and LDH. Whenever a CBC is indicated, this will include differential and platelet count. This plan is summarized in the Schema.

Because one biomarker endpoint is to evaluate metastatic tissue prior to and after treatment, patients with disease amenable to biopsy will initially be required to undergo one pretreatment biopsy and one post-treatment biopsy roughly three months after the start of treatment. It is our intent to have at least 6 patients per study arm with evaluable pre-treatment and post-treatment

biopsies. If this is reached, subsequent patients with viable lesions amenable to biopsy may not be required to undergo these procedures. It is expected that some patients may have a baseline biopsy and not be able to undergo a repeat biopsy, and some patients may not have viable disease to biopsy, and these instances will not affect study participation. Similarly, up to 6 subjects per arm will be required to complete the FLT PET scan at baseline and again at month 3 (Week 12). If there are subjects who complete the first but not the second scan, more than 6 subjects in an arm may, after approval from the Study PI, undergo the FLT PET scans in order to have at least 6 subjects who complete both scans. A maximum of 10 evaluable subjects between Arms 3 and 4 will be required to undergo the NaF PET scans. Selected subjects in Arm #3 will undergo either the FLT PET or the NaF PET based on the area of their disease (soft tissue vs bone). Subjects in Arm 4 will not receive additional biopsies but may undergo NaF PET.

FIRST COHORT: STUDY ARMS 1 and 2:

A. Prescreen / Eligibility (performed within 6 weeks of Day 1)

1. Confirm potential eligibility by history, pathology, diagnosis; no exclusions by history
2. CT scan of abdomen and pelvis, bone scan
3. Sign consent form
4. Evaluation of CBC, chemistry panel, serum prostate specific antigen (PSA), serum PAP, and serum testosterone.

B. Pre-Treatment Evaluations (within 4 weeks of Day 1; can coincide with prescreen evaluation)

1. Physical examination, symptoms assessment, and ECOG performance score
2. Randomization – treatment arm assignment

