One of the best PET imaging agents for detection of bone metastasis is ^{18}F -Sodium fluoride (NaF). NaF uptake is characterized by high and rapid bone uptake accompanied by very rapid blood clearance, which results in a high bone-to-background ratio in a short time. The retention and clearance mechanisms of NaF are well understood (16). NaF retention is a 2-phase process (17). NaF is rapidly taken up by the bone, which leads to rapid clearance from the plasma. It is cleared from plasma in a biexponential manner -- the first phase has a half-life of 0.4 h, and the second phase has a half-life of 2.6 h (18). Retention of NaF in the bone is almost perfect -- essentially all the NaF that is delivered to bone by the blood is retained in the bone (19), illustrated by the fact that one hour after administration of NaF, only about 10% of the injected dose remains in the blood (20). In the first phase, the $^{18}\text{F}_2$ ion exchanges for an OH_2 ion on the surface of the hydroxyapatite matrix of bone. In the second phase, the $^{18}\text{F}_2$ ion migrates into the crystalline matrix of bone, where it is retained until the bone is remodeled; therefore its retention directly reflects active bone metabolism. As a result, its accumulation is proportional to both blood flow and osteoblastic (metabolic) activity; thus, it represents an excellent PET tracer for imaging of bone metastasis (21, 22). NaF PET has been validated clinically as a diagnostic imaging modality. In this context, NaF PET has been shown to be superior to both FDG PET and $^{99\text{m}}\text{Tc}$ -MDP SPECT in detection of bone metastases (16, 25). NaF is a FDA approved imaging tracer for use with PET/CT. We hypothesize that NaF PET/CT will be able to detect early changes in number of bone metastases, as well as changes in osteoblastic activity that may reflect inflammatory effects. Three NaF PET/CT will be obtained in 6 - 10 patients with known osteoblastic metastases (baseline, at week 6 (+/- 1 wk), and again at week 12 (+/- 1 wk)).

Sodium Fluoride F 18 (NaF) Injection

NaF is commercially available. Ordering, Dosimetry, Quality Assurance, Quality Control, and Storage will be per usual protocols.

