This section outlines the statistical analysis strategy and procedures for the study. Prior to the analysis of the final study data, a detailed Statistical Analysis Plan (SAP) will be written describing all analyses that will be performed.

Summary tabulations will be presented that will display the number of observations, mean, standard deviation, median, range, minimum, and maximum for continuous variables and the number and percent per category for ordinal and categorical data. All endpoints of this study will

be presented graphically where possible using boxplots and histograms for continuous variables and (stacked) bar charts for categorical variables. Data analysis will be performed using SAS[®] (SAS Institute Inc., Cary, North Carolina) version 9.3 or greater.

There are many comparisons made between the two trial arms for multiple measurements, both clinical and laboratory. However, since this a pilot study, no adjustment will be made for multiple comparisons. A two-sided test at a significance level of 0.05 will be used for all comparisons, unless noted otherwise.

F.2. Analysis Populations

The ITT population consists of all patients who are randomized. The per-protocol population consists of all evaluable patients, i.e., patients who have been treated according to protocol (all inclusion/exclusion criteria are satisfied, and adequate treatment compliance (complete treatment to at least day 43). The safety population consists of all subjects who received at least one dose of pTVG HP alone or in combination with pembrolizumab. All primary, secondary and correlative outcomes will be analyzed for both the IIT and per-protocol population. The IIT population will be the primary analysis population. Safety will be evaluated using the safety population.

F.3. Baseline Comparability

All measurements (variables) collected at baseline will be summarized and compared between study arms. These include demographic variables, ECOG PS, lab parameters (CBC, chemistry panel, serum testosterone, PSA and PAP) medical history information and CTCs. Comparisons between study arms of baseline variables on a continuous scale will be performed using a two-sample t-test and/or nonparametric Wilcoxon Rank Sum test. Comparisons between study arms of baseline variables on a categorical scale will be performed using Fisher's exact test.

F.4. Analysis of Primary Endpoints

F.4.1. Analysis of Toxicity Rates and Serum Chemistry Parameters

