Linear regression analysis will be conducted to determine whether treatment with either sequence elicits other regulatory molecules on tumor-specific T cells or tumor cells.

F.6.6. Evaluation whether PD-1-Regulated Antigen-specific T-cells Identified by *trans vivo* DTH Testing Can Identify Patients who Develop Objective Clinical Responses with PD-1 Blockade Therapy in Combination with pTVG-HP

The number and frequencies of PD-1-regulated antigen specific T-cell responses will be summarized in tabular format. Logistic regression analysis will be conducted to examine whether PD-1 regulated antigen-specific T-cells predict clinical response. The sensitivity, specificity, negative predictive value and positive predictive value of PD-1 regulated antigen specific T-cell responses for predicting clinical response will be calculated and reported along with the corresponding 95% confidence intervals.

F.6.7. Evaluation of changes in FLT uptake by FLT PET/CT after Treatment with pTVG-HP with or without Pembrolizumab

Standard PET parameters, including SUV_{total} , SUV_{max} , SUV_{mean} , and the number of lesions, in terms of soft tissue lesions and major lymph node groups, will be obtained. Parameters will be summarized in terms of means, standard deviations and ranges. Within each arm and for both arms combined, changes in parameters will be evaluated using a paired t-test (for SUV) or nonparametric Wilcoxon signed rank test (number of lesions). Since the distribution of SUV values is generally skewed, a log-transformation will be utilized before conducting the comparisons. A two-sample t-test or nonparametric Wilcoxon rank sum test will be used to compare changes in parameters between study arms.

F.6.8 Evaluation of changes in NaF uptake by NaF PET/CT after treatment with pTVG-HP with or without Pembrolizumab

Standard PET parameters, including SUV_{total} , SUV_{max} , SUV_{mean} , and the number of lesions, in terms of osteoblastic lesions, will be obtained using established PERCIST criteria. To ensure uniformity, the established UW Nuclear Medicine image acquisition and reconstruction procedures for NaF PET/CT will be utilized. Please refer to the UW Nuclear Medicine Standard Operating Procedure for image acquisition and other image-related details. Image analysis will be performed in Nuclear Medicine and led by [name] (co-investigator).

12. Administrative Considerations

A. Specimen Handling

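### The NaF PET power statement does not tie sample size to effect size: under a paired t-test, 80% power at an effect of 1.0 needs all 10 patients, and six patients detect about 1.44

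*Combined protocol and SAP*

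**What the plan says.** The last paragraph of section 11.E sets the size of the NaF substudy: "NaF PET/CT will be obtained in 6 - 10 patients with known osteoblastic metastases at baseline, week 6 and week 12". It then states the power: "This sample size will provide at least 80% power to detect moderate to large effect sizes ranging from 1.0-2.0", and completes the sentence with "for the differences in SUV metrics between time points at the two-sided 0.05 significance level".

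Section 10.F repeats the number of patients: "Three NaF PET/CT will be obtained in 6 - 10 patients with known osteoblastic metastases". Section 9 makes ten an upper limit over two arms together: "A maximum of 10 evaluable subjects between Arms 3 and 4 will be required to undergo the NaF PET scans". Any number from 6 to 10 therefore complies with the plan, and section 9 does not require more than 10 evaluable patients.

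The test for NaF has to be inferred. Section 11.F.6.7 covers FLT PET and says that "changes in parameters will be evaluated using a paired t-test (for SUV) or nonparametric Wilcoxon signed rank test (number of lesions"), with SUV log-transformed first. Section 11.F.6.8 covers NaF PET and lists the parameters to be obtained, but names no test and no transformation. Section 11.F.1 says that "no adjustment will be made for multiple comparisons".

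**The concern.** One power figure is attached to a range of sample sizes and a range of effect sizes, and nothing links the two. A reader can take it that any permitted number of patients gives at least 80% power anywhere between 1.0 and 2.0. With so few patients, the detectable effect changes a good deal between 6 and 10, so this reading needs checking at its least favourable corner: 6 patients and an effect of 1.0.

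What is at stake is how a non-significant SUV change would be interpreted. If 6 to 8 patients are scanned and the result is set against a stated power of at least 80% at 1.0, the absence of a detected change could be given more weight than the data allow. The plan does not say that it will be used this way. The risk is that the sentence is carried unchanged into the detailed SAP promised in section 11.F.1 or into a report.

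**Working it through.** **Inputs from the documents**
- Number of patients n: 6 to 10 (sections 11.E and 10.F), with 10 as the maximum (section 9).
- Significance level: two-sided 0.05, for differences between time points (section 11.E).
- Stated power and effect: at least 80% for 1.0 to 2.0 (section 11.E).

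**Assumptions, because the documents do not settle them**
- Test: paired t-test. It is named for FLT in 11.F.6.7; 11.F.6.8 names none for NaF.
- Effect size d = mean within-patient change / SD of that change. Section 11.E does not define the standardizing SD.
- Changes approximately normal on the scale analysed (raw or log SUV).

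**Formula.** With df = n − 1, noncentrality d√n and critical value c = t(0.975, n − 1),

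power = P(T > c) + P(T < −c), where T is noncentral t with df and noncentrality as above.

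**Step 1: the plan's own figure.** For n = 10 and d = 1.0: c = 2.262, noncentrality = 1.0 × √10 = 3.162, power = 80.3%. The stated 80% at an effect of 1.0 is reproduced with 10 patients.

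**Step 2: the other permitted sizes.** For n = 6 and d = 1.0: c = 2.571, noncentrality = √6 = 2.449, power = 50.7%. The full set, with the effect at which power reaches 80%:

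| n | Power at d = 1.0 | Power at d = 1.5 | Power at d = 2.0 | d for 80% power |
|---|---|---|---|---|
| 6 | 50.7% | 83.3% | 97.1% | 1.435 |
| 7 | 60.0% | 90.8% | 99.1% | 1.273 |
| 8 | 68.1% | 95.1% | 99.8% | 1.157 |
| 9 | 74.8% | 97.5% | 99.9% | 1.067 |
| 10 | 80.3% | 98.7% | >99.9% | 0.997 |

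Rounded up so that power is not below 80%, the detectable effects are 1.44, 1.28, 1.16, 1.07 and 1.00. Rounding down at n = 6 to 1.43 gives 79.8%.

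**Step 3: sensitivity to the assumptions, at n = 6 and d = 1.0**
- One-sided t-test: 67.7%. Normal approximation, two-sided: 68.8%. The normal approximation passes 80% at n = 8 (80.7%) but is not suitable for samples this small.
- Wilcoxon signed-rank test: about 35%. With six patients the smallest two-sided p-value is 2/2⁶ = 0.031 and the next is 4/2⁶ = 0.0625, so significance needs all six changes in the same direction. For normal changes, 80% power then needs Φ(d)⁶ = 0.80, ignoring the negligible opposite tail, which gives d of about 1.79. At d = 2.0 the power is about 87%.
- Effect standardized by the SD of a single measurement, with correlation ρ between time points: the effect in units of the SD of change is 1/√(2(1 − ρ)). Power is 29% at ρ = 0, 51% at ρ = 0.5 and 87% at ρ = 0.8.

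**The case against.** The strongest defence is that the two ranges are meant to be read together: 10 patients go with 1.0, and fewer patients go with larger effects. On that reading the sentence is true. Ten patients give 80.3% at 1.0, and six give 97.1% at 2.0. The detectable effect with 10 patients is 0.997, which matches the stated lower end and makes this intention plausible. Because the claim is for at least 80%, an upper end above the true detectable effect is conservative and not an arithmetic error. A signed-rank test with 6 patients would need about 1.79, so 2.0 is not an absurd limit.

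Most of this stands. A reader might infer that the power statement is simply false below 10 patients. The documents do not support that. Section 11.E nowhere says that six patients give 80% power at 1.0, and even if every sample size is crossed with every effect, the claim holds for effects of about 1.44 to 2.0 with 6 patients and about 1.07 to 2.0 with 9. A reader might also treat 51% as the power of the design. It is conditional on a test and an SD that the plan does not specify for NaF, and with the single-measurement SD the figure could lie anywhere from 29% to 87% for correlations of 0 to 0.8.

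What the defence does not remove is the gap in the text. The sentence refers to the whole range of sample sizes and links no number of patients to any effect. Under the paired t-test, 2.0 is not the 80% effect for any permitted number of patients. The reader has to reconstruct the pairing.

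**Conclusion.** The point holds as a lack of precision in an exploratory power statement. Under a paired t-test at two-sided 0.05, with the effect standardized by the SD of the within-patient change, 80% power at an effect of 1.0 requires all 10 patients. A reader who relied on 80% at 1.0 with six patients would overstate the power by about 29 percentage points (80 − 51). The effect detectable with 80% power at six patients is about 1.44.

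The arithmetic is firm given those assumptions. The assumptions themselves are not in the plan for NaF, and that is part of what needs repair. Practical importance is low: NaF imaging is exploratory objective 8, section 6.B keeps these scans out of individual treatment decisions, and no primary conclusion depends on this power.

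**What to change.** Replace the power sentence in section 11.E with: *With a paired t-test (two-sided 0.05), the substudy has 80% power to detect a mean change in SUV, in units of the SD of the change, of about 1.44 with 6 patients and 1.0 with 10 patients.*

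In section 11.F.6.8, name the same test and state whether SUV is analysed on the raw or the log scale. Log transformation is currently specified for FLT only, so using it for NaF would be a choice to declare. If the signed-rank test is intended for SUV, the figures above do not apply and should be recalculated for that test.

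The cost is one replaced sentence in 11.E and one added in 11.F.6.8. No patient, scan or design feature changes.
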